In a Phase 3 trial, patients were treated with chlorambucil alone, GAZYVARO in combination with chlorambucil, or rituximab product in combination with chlorambucil. The Stage 1 analysis compared GAZYVARO in combination with chlorambucil vs. chlorambucil alone, and Stage 2 compared GAZYVARO in combination with chlorambucil vs. rituximab product in combination with chlorambucil.

The most common Grade 3 to 4 adverse reactions (incidence $\geq 10\%$) observed in patients with CLL in the GAZYVARO containing arm of clinical trials were neutropenia, infusion reactions, and thrombocytopenia.

The most common adverse reactions (incidence $\geq 10\%$) observed in patients with CLL in the GAZYVARO containing arm were infusion reactions, neutropenia, thrombocytopenia, anemia, pyrexia, cough, nausea, and diarrhea.

The most common obinutuzumab-related events are infusion-related reactions and tumor lysis syndrome, most commonly during the initial administration, hypersensitivity (immediate or delayed onset), and worsening of pre-existing cardiac conditions. Some patients receiving obinutuzumab have experienced cytopenias or infections. Obinutuzumab use has been associated with hepatitis B virus (HBV) reactivation and very rare cases of progressive multifocal leukoencephalopathy. Mitigation strategies are defined in this protocol. To reduce the incidence and severity of obinutuzumab-related infusion reactions, established premedication regimens and infusion modification algorithms have been included (Section 5.3.2). To mitigate the risk of *Pneumocystis jirovecii* pneumonia, antibiotic prophylaxis is required (Section 5.4.1).

To mitigate the risk of HBV reactivation in subjects treated with an anti-CD20 antibody, HBV screening will be performed. Subjects who are hepatitis B core antibody positive at screening may be enrolled only if the plasma DNA PCR test is negative, and will be monitored for potential HBV reactivation (manifested as detectable HBV DNA by quantitative PCR). Subjects will be tested monthly for the duration of obinutuzumab therapy and every 3 months thereafter for 1 year from the last dose of obinutuzumab therapy in this study. Specific instructions for supportive care in response to myelosuppression are described. Investigators are instructed to institute prophylaxis and monitoring for tumor lysis syndrome for subjects with a high tumor burden, high circulating lymphocyte count ($>25 \times 10^9/L$) or renal impairment ($CrCl < 70 mL/min$).

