3.5. Duration of Study

This study will continue to monitor subjects for up to 30 days post end of treatment, or up to Week 25 should a subject discontinue treatment prior to Week 25 for reasons other than disease progression.

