6.6.4. Hepatic Events

Transaminase Elevations: Reversible asymptomatic ALT/AST increases have been observed with idelalisib in subjects with hematologic malignancies. Transaminase elevations generally occurred within 4 to 12 weeks of drug initiation, and resolved spontaneously over a period of 2 to 4 weeks with drug being continued for Grade 1 and 2 elevations and drug withheld for Grade 3 or 4 elevations until resolution. Transaminase elevations are most frequently asymptomatic, transient and occurring within the first 3 months of treatment.

Successful rechallenge after resolution at either the same or lower dose level of idelalisib has been achieved in the majority of subjects. There has been no evidence of impaired synthetic function. Close monitoring of hepatic laboratory tests during therapy is important to allow for appropriate idelalisib interruption and reinstatement so that subjects may continue with study drug treatment.

HBV Reactivation: HBV reactivation can occur with treatment, most commonly in patients treated with obinutuzumab. The risk is very low among patients with negative anti-HBc serology and/or undetectable HBV DNA as assessed by quantitative PCR. Although some subjects who are HBc antibody positive with negative PCR may have had passive transfer of antibody from intravenous IgG, it cannot be known for certain that any such subject did not have natural HBV infection. Therefore, all subjects who are HBc antibody positive at screening will be monitored for potential HBV reactivation (manifest as detectable HBV DNA by quantitative PCR). Surveillance of subjects who test positive for HBc antibody for HBV reaction will be performed according to the Study Procedures Table ([Appendix 2](#)). If there is evidence of HBV reactivation immediately stop study treatment and start appropriate treatment for HBV. In the event of HBV reactivation, please contact the Medical Monitor prior to re-initiation of study treatment.

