2. Screening and End of Treatment will be complete physical examinations. Beginning at Week 1 Day 1, a modified physical examination will be a performed to monitor for any changes (eg, lymph nodes, size of the liver and spleen, lung, cardiac, abdomen, skin, neurologic, and any system clinically indicated). Weight should be measured at each PE. Height should be measured at screening only.
3. The G8 screening questionnaire will be used for assessment of subjects aged > 70 years at Week 1 Day 1 and every 6 months until EOT.
4. Subjects should be resting quietly in supine position for 5 minutes prior to ECG collection. The Investigator or qualified designee will review all ECGs.
5. Study drug is not dispensed at the Week 105 visit.
6. Obinutuzumab: 100 mg will be administered intravenously on Day 1 and 900 mg on either Day 1 or 2 (Week 1); then 1000 mg on Day 8 (Week 2), Day 15 (Week 3), and on Weeks 5, 9, 13, 17 and 21 for a total of 8 doses of 1000 mg over 21 weeks. If the 100 mg infusion on Day 1 is well tolerated, the remaining 900 mg (scheduled for Day 2) may be given on Day 1.
7. CBC with differential should be obtained every 2 weeks through Week 25 to evaluate for neutropenia and then at subsequent visits for assessment.

8. Peripheral blood MRD will be assessed on Day 1 of Weeks 1, 13, 25, 33, 45, 105, and EOT. EOT collection is not needed for subjects who complete the Week 105 visit.
9. Serum pregnancy test will be performed at screening for all women of childbearing potential (defined in [Appendix 4](#)). Urine pregnancy tests will be conducted prior to Week 1, Day 1 and then every 4 weeks until the EOT visit. Pregnancy kits may be provided for home testing. The results must be confirmed as negative prior to continued administration of study drug.
10. Hepatitis serology includes HBsAg, HBcAb, HCV Ab; patients with positive HBcAb and negative HBsAg should have HBV DNA PCR performed prior to treatment start to rule out occult infection, then monthly through 6 months and then at subsequent clinic visits until EOT visit. HIV testing and CMV IgG and IgM testing should be performed at screening.
11. CMV antigen or quantitative PCR testing should be performed at screening and according to the schedule of assessments throughout the course of idelalisib treatment.
CCI [REDACTED]
- CCI [REDACTED]

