14. CLL immunophenotyping, karyotyping and FISH, TP53 and IgHV mutation status, CD38 and ZAP70 expression will be evaluated from peripheral blood at screening. In the event of disease progression, only FISH and TP53 will be evaluated.
15. Tumor evaluation by CT scan (preferred) or MRI of neck, chest, abdomen, and pelvis will be performed at screening (unless scan was already completed up to 42 days prior to first dose). At the Week 25 visit, the same type of evaluation should be performed on those body regions which showed involvement by CLL at screening. An additional CT may be obtained on protocol per investigator discretion following evidence of an improvement in clinical response if the response assessment at the Week 25 visit is less than a complete response or in the event of suspected disease progression.
16. A bone marrow evaluation is required in the screening window for subjects without radiographic evidence of disease. Bone marrow aspirate and biopsy should be performed at Week 25 for subjects fulfilling clinical response criteria for CR or CRi per the modified IWCLL 2008 criteria. MRD should be assessed from bone marrow aspirate at the reference laboratory in Kiel; CCI [REDACTED]
CCI [REDACTED]
17. Qualitative treatment response assessment based on physical exam, laboratory parameters and presence of B symptoms should be performed every 4 weeks until Week 33 Day 1 and then at all scheduled visits thereafter following the modified IWCLL 2008 criteria, with the exception of lymphadenopathy, hepatomegaly, splenomegaly, and bone marrow. Assessment of response per modified IWCLL 2008 criteria should also be recorded at the completion of 24 weeks on treatment and subsequent to any CT and/or bone marrow biopsy that is repeated while on study.
18. Following evaluation of the safety data for the first 6 subjects enrolled in each treatment arm, the Safety Review Team (SRT) will determine if weekly clinical evaluation should continue for the duration of the study.
19. The EOT visit should be scheduled for approximately 30 days following discontinuation of all study treatment. For subjects that permanently discontinue all treatment prior to Week 25 Day 1, the Week 25 Day 1 visit should also be performed and may satisfy the requirement for the EOT visit if falling into the +30 days \pm 7 day window from all study drug discontinuation.

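### HBV DNA testing promised for a year after the last obinutuzumab dose ends at the EOT visit, so subjects who stop all treatment early lose part or most of it

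*Protocol*

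**What the plan says.** Protocol Section 1.6 names HBV reactivation as a recognised obinutuzumab risk and lists the mitigation. Core-antibody-positive subjects enter only with a negative HBV DNA PCR. They are then tested monthly while on obinutuzumab and "every 3 months thereafter for 1 year from the last dose of obinutuzumab therapy in this study".

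Section 6.6.4 gives the operative instruction: "Surveillance of subjects who test positive for HBc antibody for HBV reaction will be performed according to the Study Procedures Table". In that table (Appendix 2, footnote 10), HBV DNA PCR is done before treatment, "then monthly through 6 months and then at subsequent clinic visits until EOT visit". Footnote 10 of SAP Appendix 1 repeats this.

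Footnote 19 of Appendix 2 fixes the end point: "The EOT visit should be scheduled for approximately 30 days following discontinuation of all study treatment". Section 3.5 closes follow-up at the same time: "This study will continue to monitor subjects for up to 30 days post end of treatment". Its one exception keeps subjects who stopped earlier without progression under observation until the Week 25 visit. Section 3.2 records that Amendment 4 removed the Post Treatment period, and Sections 3.8 and 6.9 plan no care after the study. Section 3.3 requires oral treatment to stop 3 months after CR/BM MRD- is documented, or at 104 weeks if that comes first.

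**The concern.** The two texts run on different clocks. Section 1.6 counts from the last obinutuzumab dose. Appendix 2 counts from the stop of all study drugs. They agree only for subjects who stay on the oral drugs long enough. A site that follows the schedule exactly has no visit at which to take the remaining samples from anyone who stops earlier.

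What is at stake is a stated safety measure. Section 6.6.4 puts the risk in proportion, "The risk is very low among patients with negative anti-HBc serology and/or undetectable HBV DNA as assessed by quantitative PCR", but still requires every core-antibody-positive subject to be monitored, because past natural infection cannot be ruled out. AE collection stops 30 days after the last dose, and investigators need not look for SAEs after the study ends. Reactivation after EOT would therefore be found only if it became clinically apparent or was tested for elsewhere.

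One group loses coverage by protocol rule and not by misfortune: deep responders, the outcome the trial hopes for, are told to stop.

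**Working it through.** **Inputs.** Week w Day d is study day 7(w − 1) + d.

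- Obinutuzumab doses (Appendix 2, footnote 6): Weeks 1, 2, 3, 5, 9, 13, 17 and 21. That makes 8 doses with the last at Week 21, matching the plan's stated 8 doses over 21 weeks.
- EOT: 30 days after all drugs stop, visit window ±7 days.
- Week 25 marrow window (footnote 21; the sign is legible in the SAP copy): −7 to +14 days.
- Assumption: 3 months = 91 days for the CR/BM MRD- stop.

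**The promised year.** Last dose: 7 × 20 + 1 = day 141. Year end: 141 + 365 = day 506 (Week 73).

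**Cutoffs.**

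- Full coverage needs a stop no earlier than 506 − 30 = day 476, the end of Week 68. With EOT at +37 or +23 days, this moves to day 469 or 483 (end of Week 67 or 69).
- More than half is lost if stop + 30 < 141 + 182.5 = 323.5, that is, a stop before day 293.5, about Week 43 (day 286.5 to 300.5 over the EOT window).

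**Loss by time of stopping, full obinutuzumab course.**

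| Stop | EOT day | Days covered | Days lost of 365 |
|---|---|---|---|
| Week 25 Day 1 (day 169) | 199 | 58 | 307 (84%) |
| CR/BM MRD-, marrow at −7 days (stop day 253) | 283 | 142 | 223 (61%) |
| CR/BM MRD-, marrow on day 169 (stop day 260) | 290 | 149 | 216 (59%) |
| CR/BM MRD-, marrow at +14 days (stop day 274) | 304 | 163 | 202 (55%) |
| Week 52 Day 1 (day 358) | 388 | 247 | 118 (32%) |
| Week 64 Day 1 (day 442) | 472 | 331 | 34 (9%) |
| Week 68 Day 1 (day 470) | 500 | 359 | 6 (2%) |

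The CR/BM MRD- rows count from marrow sampling. Each week between sampling and documentation lowers the loss by 7/365 = 1.9 points.

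**Tests that still happen.** After a Week 25 stop: Week 25 (28 days after the last dose) and EOT (58 days). On the CR/BM MRD- route: Weeks 25, 29 and 33 (28, 56 and 84 days) and EOT. With marrow on day 169 or later, that EOT falls in Weeks 42 to 44. A 3-monthly grid from day 141 (steps of 365/4 = 91.25 days) falls in Weeks 34, 47, 60 and 73. All four points come after EOT in the first case, and three in the second.

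**Obinutuzumab also stopped early.** Take the last dose and all drugs stopping at Week 13 (day 85) without progression. If the Week 25 visit required by Section 3.5 carries a test, 169 − 85 = 84 days are covered and 281/365 = 77% is lost. If testing ends at EOT (day 115), 30 days are covered and 335/365 = 92% is lost.

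**How many subjects.** The documents give neither core-antibody prevalence nor an early-stop rate. Assume 1% to 10% prevalence and, independently, 10% to 50% stopping early enough to lose some coverage. For 30 Arm B subjects:

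- Expected number: 30 × 0.01 × 0.10 = 0.03 to 30 × 0.10 × 0.50 = 1.5.
- Chance of at least one: 1 − 0.999^30 = 3% to 1 − 0.95^30 = 79%.

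**The case against.** The best counter-argument is that the conflict alone does not show which text is out of date. Section 6.6.4, Appendix 2, its SAP copy, Section 3.5 and the removal of the Post Treatment period all point one way. The Section 1.6 sentence could be a leftover, and deleting it would restore consistency. That is possible, but it would remove a safeguard presented as part of the risk mitigation, with nothing in its place.

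A second argument is that investigators are bound by the whole protocol (Section 9.1.9), so Section 1.6 applies directly, and Section 6.3 asks for follow-up to continue after dosing stops. But Section 6.3 covers only required procedures, and neither section creates a visit or a sample after participation has ended. The registry is non-interventional and does not fill the gap.

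Several points of scale stand:

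- Losses for stops near Week 68 are a few days, inside the EOT window.
- In the Week 13 example, 77% is the better reading, since the Week 25 visit is required and footnote 10 tests monthly through 6 months.
- A CR/BM MRD- subject still has four tests after the last dose, though all in the first part of the year.
- The 3% to 79% range counts any loss, however small, and rests on assumed rates.
- Table 6-1 and some Appendix 2 footnotes are redacted, and the obinutuzumab labelling is not in the documents, so a provision there cannot be excluded.

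**Conclusion.** The concern holds. The readable schedule does not deliver the year of HBV DNA testing that Section 1.6 promises. It affects only core-antibody-positive, HBV DNA-negative subjects who receive obinutuzumab and stop all treatment early. After a full course, the loss is 84% of the year for a Week 25 stop and 55% to 61% for the required stop after a Week 25 CR/BM MRD-. It falls below half from about Week 43 and reaches zero at the end of Week 68. These figures assume EOT at 30 days and, for the CR/BM MRD- stop, documentation at the time of marrow sampling. The number of subjects is small and may be zero. No efficacy analysis is touched, and HBV DNA is not among the laboratory tests in SAP Appendix 9. It should be corrected because it concerns patient safety and the correction is cheap.

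**What to change.** Amend Appendix 2 footnote 10 and Section 6.6.4 to say that core-antibody-positive subjects who received obinutuzumab have HBV DNA PCR every 3 months until 12 months after their last obinutuzumab dose, regardless of EOT. Add this to Section 3.5 as a second exception beside the Week 25 provision.

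State who acts on a positive result after EOT. The present instruction, "If there is evidence of HBV reactivation immediately stop study treatment and start appropriate treatment for HBV", is written for someone still on treatment. Update the SAP copy of the schedule for consistency only.

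The cost is protocol wording plus about four draws after EOT for a Week 25 stop, or three on the CR/BM MRD- route, with those few subjects followed for up to 12 months after their last obinutuzumab dose. Section 1.6 already promises these tests. The protocol already sets duties beyond EOT (PJP prophylaxis for 2 to 6 months after idelalisib, contraception to 18 months after obinutuzumab), although those need no study sample. No analysis changes.

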1.7. Compliance

This study will be conducted in compliance with this protocol, Good Clinical Practice (GCP), and all applicable regulatory requirements.

2. OBJECTIVES

The primary objective of this study is:

- To determine the preliminary efficacy of the combination of tirabrutinib and idelalisib with obinutuzumab in subjects with relapsed or refractory CLL

The secondary objective of this study is:

- To evaluate the safety and tolerability of the combination of tirabrutinib and idelalisib with and without obinutuzumab

CCI [REDACTED]

[REDACTED]

[REDACTED]

3. STUDY DESIGN

[figure not shown]
3.1. Study Design

This is a Phase 2, prospective, open-label, multicenter trial to evaluate the safety and efficacy of the combination of tirabrutinib and idelalisib with and without obinutuzumab in subjects with relapsed or refractory CLL.

[figure not shown]
3.2. Study Treatments

Combination therapy of tirabrutinib (BTK inhibitor) 80 mg once daily and idelalisib (PI3K δ inhibitor) 100 mg once daily with and without obinutuzumab will be evaluated for efficacy, safety, and tolerability.

[figure not shown]
Eligible subjects will be treated with the combination of tirabrutinib and idelalisib and stratified by the presence of del17p/TP53mut in CLL cells. Following stratification, subjects will be randomized 1:1 to treatment with the combination of tirabrutinib and idelalisib with or without obinutuzumab.

With Amendment 3, randomization was discontinued. All subsequently enrolled subjects entered Arm B (tirabrutinib + idelalisib + obinutuzumab).

With Amendment 4, the Post Treatment period will no longer be applicable.

Enrollment will be temporarily paused following enrollment of the first 6 subjects into Arm B, who will be observed for safety for 28 days following the first dose of study treatment including weekly clinical evaluation through that period. Additional subjects may be enrolled into the safety cohort if any of the first 6 subjects in Arm B discontinue therapy during the initial 28 days for reasons unrelated to toxicity. A Safety Review Team (SRT) will review 28-day safety data from the first 6 subjects in Arm B and determine whether enrollment may resume and if weekly clinical evaluation through the first 28 days should continue or may be reduced in frequency for the remainder of the subjects enrolled in the study.

The SRT will consist of at least one investigator from the GCLLSG and Gilead study team members including but not limited to: the medical monitor, representatives from Pharmacovigilance and Epidemiology (PVE), and Biostatistics.

The safety review will include the assessment of the following:

- Grade ≥ 4 hematological toxicities persisting for > 7 days or non-hematologic laboratory abnormalities except for asymptomatic AST/ALT elevation
- Grade ≥ 3 non-hematological toxicities (except for alopecia or the following that resolve within 72 hours with medical intervention: tumor lysis, nausea, vomiting, diarrhea, or constipation)
- Grade ≥ 2 non-hematologic treatment-emergent adverse events (TEAE) that in the opinion of the investigator are of potential clinical significance such that further dosing would expose subjects to unacceptable risk

Criteria for termination of the study are:

- 1) An unacceptable safety profile or incidence of AEs or SAEs revealed in this or any other study in which the combination of agents is administered
- 2) Any other factor that in the view of the sponsor constitutes an adequate reason for terminating the study

As agreed with the German Federal Institute for Drugs and Medical Devices Agency (BfArM), safety report including the cumulative safety results and summary of the conclusion of the SRT following assessment of the safety cohort was submitted to the BfArM.

The study steering committee, including representatives from the GCLLSG and Gilead, will review ongoing safety data at least quarterly throughout the treatment period and regularly for the complete duration of the study.

3.3. Duration of Treatment

Obinutuzumab will be administered for up to 8 doses over 21 weeks to subjects randomized or enrolled to Arm B (tirabrutinib + idelalisib + obinutuzumab). Combination treatment with the oral agents (tirabrutinib and idelalisib) will continue for all subjects for up to 104 weeks in the absence of disease progression, unacceptable toxicity, or documentation of CR/BM MRD-. If CR/BM MRD- is documented on study, treatment will stop after the earlier of:

- A) an additional 3 months of therapy or
- B) 104 weeks of total treatment

3.4. Criteria for Discontinuation of Study Treatment

Study medication may be discontinued in the following instances:

- Documented progression of CLL
- Non-study treatment for CLL
- Development of malignant disease requiring systemic therapy
- Pregnancy
- Investigator discretion
- Non-compliance with study treatment
- Severe protocol violation
- Subject request to discontinue for any reason
- Lost to follow-up
- Death
- Study termination by the sponsor
- Intercurrent illness that would, in the judgment of the investigator, affect assessments of clinical status to a significant degree
- Unacceptable toxicity, as defined in the toxicity management section of the protocol (Section 6.5), or toxicity that, in the judgment of the investigator, compromises the ability to continue study-specific procedures or is considered to not be in the subject's best interest

3.5. Duration of Study

This study will continue to monitor subjects for up to 30 days post end of treatment, or up to Week 25 should a subject discontinue treatment prior to Week 25 for reasons other than disease progression.

3.6. Criteria for Discontinuation from Study

Subjects may be removed from the study for the following reasons:

- Death
- Investigator discretion
- Withdrawal of consent
- Study termination by the sponsor

